We will provide data from the 20 sites and Find and Treat to the Health & Social Care Information Centre (HSCIC). These records will be list cleaned and then linked by HSCIC to the Hospital Episode Statistics (HES) database to provide data on hospitalisations and A&E attendances and deaths for individuals in the 20 sites and Find and Treat database. In order to be able to identify co-morbidities more accurately we will request data on all previous admissions for these groups for identification of

comorbidities but analyses of admission rates will be confined to the period November 2008 – November 2016.

Study design:

We will construct a virtual cohort that will take first date of admission as the entry point (earliest November 2008) or, for control groups an admission matched by month and year restricted to individuals over the age of 18. Exit from the virtual cohort will be at the end of November 2016 or, if earlier, date of death. We will conduct person-level analyses using Poisson regression to compare overall hospitalisation rates, emergency admission rates, all cause mortality and avoidable mortality rates in:

- 1) Homeless people using the different categories of SIHCC service (clinically led services - sites 1&2, 7-13; non-clinically led services - sites 3&4, 14-20)
- 2) Find and Treat Homeless population and sites 5&6 with standard usual care
- 3) Socially deprived non-homeless population.

We will also conduct analyses at the level of the hospital admission whereby through knowledge of the dates of SIHCC involvement and service user group we will be able to classify hospital admissions in the period November 2008- November 2016) into the following groups:

- 1) Admissions in a socially deprived non homeless population
- 2) Admissions in the general homeless population (Find and Treat data)
- 3) Admissions in homeless service users prior to their first engagement with SIHCC
- 4) Admissions in homeless service users where there is evidence of SIHCC support for that admission
- 5) Admissions in homeless service users that occur following SIHCC support but where there is no record of support for the subsequent admission.

We will use Cox regression survival models and Kaplan Meir plots (accounting for clustering at the level of the hospital and individual) to explore how admissions in these groups compare in terms of the following primary outcomes:

- 1) Time from discharge to next A&E attendance

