- 2) 28 day emergency readmission rates (these are a commonly used indicator within the NHS)
- 3) Time from discharge to next hospital inpatient readmission

Secondary outcomes we will examine include:

- 1) Time from admission to death
- 2) Duration of inpatient admission
- 3) Time from admission to mortality from causes amenable to healthcare
- 4) Time from discharge to admission with ambulatory care sensitive (ACS) conditions
- 5) Time from discharge to next planned admission,
- 6) Overall readmission rates
- 7) Unscheduled readmission rates
- 8) All cause mortality
- 9) International Classification of Diseases 10th Revision chapter-specific mortality
- 10) In-patient costs using Health Resource Group

For those service users with quality of life data we will explore how this changes following involvement of services and how it compares to the measures of quality of life derived from studies within Find and Treat service users and within socially deprived non-homeless groups.

A variety of mortality groupings have been developed to identify causes of death that could be considered avoidable through better medical care depending on age at which they occur. The proposals for the Public Health Outcome Monitoring framework take a similar approach and focus on key areas of avoidable mortality namely: mortality from suicide, communicable diseases, excess

seasonal mortality and, in persons aged less than 75 years, cardiovascular disease, cancer, chronic liver disease and chronic respiratory diseases. All of these are useful indicators within homeless populations.

Sample size:

Our sample size is based upon our estimates of historical data from the two types of SIHHC services (non-clinically led SIHHC services vs. clinically led SIHHC). We estimate that each type will have data from approximately 2,208 individuals for the two-year duration of the study, based on the services seeing on average 92 people per month.

From previous health service evaluation data on homeless groups we expect hospitalisation rates to be 0.7 episodes per person-year for homeless individuals admitted to hospital. An important reduction in readmission rates would be 10%. To undertake a sample size calculation to determine the study size required to detect such a reduction in readmission rates, the following variables were defined:

μ_0 = mean readmission rate in the baseline group = 0.7 episodes per person-year

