Confounding variables: As this is a virtual cohort, we will not be able to collect a complete set of confounding variable data on individuals at entry to the study. Where data is provided by SIHHC services we will include age (year and month only), sex. As a result of the lack of baseline data will use historical HES data to determine past medical history from the age of 18 which will be used to create a variable to control for co-morbid conditions and historical hospital usage. Analyses will therefore control for age, gender, comorbidities (identified from HES data) and reason for admission, classified by Healthcare Resource Group (HRGs – groupings of treatment episodes which are similar in resource use and clinical response). Subgroup analyses will compare the different types of SIHCC services. Where provided by the SIHHC services, we will also control in subgroup analysis for medical symptoms, past use of health and social care services, mental health services, smoking, alcohol, and drug taking history, prison and homeless history, employment history.

Health Economics Analysis:

This analysis will cover three economic models. The primary analysis will be a cost effectiveness model (linked to effectiveness data described in the comparative effectiveness section). This model will take an NHS perspective, with costs based on the linked HES data analysis and outcomes based on morbidity and mortality data. Outcomes of homeless users of the two types of SIHHC service (clinically led and non-clinically led) will be compared to each other and homeless controls. Outcomes used for this analysis will include: 1. Overall hospital readmission rates; 2. Unscheduled readmission rates; 3. 28-day emergency readmission rates. Cost estimates will be calculated using national NHS

tariff data, and will include length of hospital stay, emergency admissions, and fixed and variable costs estimates for each of the SIHHC services.

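### In-patient cost priced by HRG should not be adjusted for the same admission's HRG, and length of stay should be shown with and without that adjustment

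*Protocol*

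**What the plan says.** Under Comparative Effectiveness Analysis, the paragraph headed Confounding variables states: "Analyses will therefore control for age, gender, comorbidities (identified from HES data) and reason for admission, classified by Healthcare Resource Group". It explains HRGs in the same sentence as "groupings of treatment episodes which are similar in resource use and clinical response". The rule is general, and no outcome is excepted.

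The list of secondary outcomes includes item 2, "Duration of inpatient admission", and item 10, "In-patient costs using Health Resource Group".

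Under Study design, the person-level comparison is followed by a second kind: "We will also conduct analyses at the level of the hospital admission". Admissions are sorted into five groups, one of which consists of admissions with evidence of scheme support during that same admission.

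Under Health Economics Analysis, costs rest on national "tariff data, and will include length of hospital stay, emergency admissions, and fixed and variable costs estimates for each of the SIHHC services". That sentence belongs to the economic models. It does not define secondary outcome 10.

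The protocol does not say which admission supplies the HRG covariate, what regression model is meant for in-patient cost, or whether the economic models are HRG-adjusted.

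**The concern.** One classification does two jobs. It is a covariate, and it is the stated basis on which outcome 10 is valued. In a model whose unit is the admission, reason for admission most naturally means that of the admission being analysed. Covariate and price then come from the same record, and the cost outcome is adjusted for what determines it.

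For length of stay the difficulty is milder. By the protocol's own description, an HRG groups treatment episodes partly by the resources they use. It is therefore not purely a characteristic present before the scheme could act. If scheme support during an admission changes the treatment given, and with it the HRG, that part of the effect is adjusted away.

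Cost implications across the system belong to Objective 3. The background section also leaves length of stay open: it sets an earlier review suggesting a 30% cut in bed days against a randomised trial that found no change. An adjusted cost difference near zero could be read by commissioners as a finding when it had been produced by the model.

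**Working it through.** The protocol gives no figure on this point, so there is none to reproduce. The check has an algebraic part, which needs no assumed values beyond its two conditions, and an illustration with assumed values.

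**1. Cost, one price per HRG.** Let admission i have group indicator T, HRG h and cost C = p(h). The adjusted model is

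C = βT + Σ γ(h)·1[HRG = h] + other covariates + error.

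Put γ(h) = p(h), β = 0 and all other coefficients 0. Every residual is then zero. Least squares cannot do better, and the solution for β is unique as long as some HRG contains admissions from both groups and T is not otherwise determined by the covariates. So β = 0 exactly, for any prices and any true effect. The conditions are a single price per HRG and a covariate taken from the costed admission.

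**2. Illustration.** All inputs here are assumptions; none is in the protocol. There are 10 HRGs with equal frequency and mean stays equally spaced from 2 to 14 days (overall mean (2 + 14)/2 = 8). Price is £500 plus £300 per mean day. Stay within an HRG is gamma-distributed. The scheme moves an admission to the next cheaper HRG with probability 0, 0.3 or 0.6, and each scenario has 200,000 admissions.

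Adjacent HRGs differ by 12/9 = 1.33 days and 1.33 × 300 = £400. Nine of the ten groups can move down, so the expected crude cost difference is −0.3 × 0.9 × 400 = −£108 or −0.6 × 0.9 × 400 = −£216.

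| Cost rule | HRG shift | Stay within HRG | Crude | HRG-adjusted |
|---|---|---|---|---|
| One price per HRG | 30% | unchanged | −£111 | 0.0 |
| One price per HRG | 60% | unchanged | −£215 | 0.0 |
| Price plus £250 per day beyond 2.5 × HRG mean stay | 30% | 30% shorter | −£172 | −£69 |
| Same | 60% | 30% shorter | −£292 | −£70 |

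The simulated crude values agree with the expected ones to within sampling error. With stay-dependent payments the adjusted difference is not zero, but it is no longer the total difference.

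**3. Length of stay, same set-up.** With stay 30% shorter within each HRG and no shift, the expected difference is −0.3 × 8 = −2.40 days. With a 60% shift, the mean before shortening is 8 − 0.6 × 0.9 × 1.33 = 7.28, so the difference is 0.7 × 7.28 − 8 = −2.90.

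| HRG shift | Stay within HRG | Crude (days) | HRG-adjusted (days) |
|---|---|---|---|
| none | 30% shorter | −2.40 | −2.40 |
| 30% | 30% shorter | −2.65 | −2.35 |
| 60% | 30% shorter | −2.90 | −2.26 |
| 30% | unchanged | −0.36 | 0.01 |

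Most of the difference survives unless it runs wholly through a change of HRG.

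**4. Direction.** Suppose the scheme instead moved admissions up, because treatment was completed, raising the expected stay from 8 to 8.72 days, while stay within each HRG fell by a factor 8/8.72 = 0.917. The crude difference would be 0, while stay within every HRG would be about 8% shorter. The adjusted estimate would then lie further from zero than the crude one. The direction of the distortion is therefore not fixed.

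**The case against.** The strongest reply is that HRG is there for a good reason. The background section attributes homeless patients' long stays largely to complexity of need, and scheme admissions are compared with those of a deprived non-homeless population. Case-mix control is essential, and stay within an HRG is a legitimate case-mix-adjusted measure. This stands for length of stay, and it is why HRG should not simply be removed there.

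A second reply is that exact zero needs two things the protocol does not state: one price per HRG, and a covariate drawn from the costed admission. This also stands as a limit on the size. It does not rescue the rule, since the admission-level reading is the natural one and stay-dependent pricing still distorts the result.

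A third reply is that outcome-specific covariate sets are usually left to the statistical analysis plan, which is not at hand. But the protocol does fix a covariate set here, and for outcome 10 it fixes it badly.

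A reader might infer more than this, and the document does not support it:

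- *That adjustment erases any length-of-stay difference, or always pulls it towards the null.* HRGs are similar in resource use, not identical, and steps 3 and 4 of the check show otherwise.
- *That the economic models are undermined.* Nothing says they are HRG-adjusted, and their costs include stay, emergency admissions and scheme costs.
- *That the readmission outcomes are over-adjusted because HRG is a mediator.* The background names early self-discharge as a problem, but it does not say that a scheme would alter HRGs. Nine of the 18 schemes are non-clinical, which makes such a shift less plausible there. For events after discharge, the index HRG is an ordinary case-mix covariate.

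**Conclusion.** For outcome 10 the stated rule is circular when applied in an admission-level model to the same admission's HRG. The adjusted difference is exactly 0 under one price per HRG, and reduced or otherwise distorted if payments also depend on stay. Only the exact zero is independent of the assumed values; the pound and day figures are illustrations.

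For outcome 2 the adjustment may remove whatever part of an effect runs through a change of HRG. That share could lie anywhere from 0 to 100%; the protocol gives no figure, and the direction of the distortion is open.

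Two of the ten secondary outcomes are affected, only one of them by circularity. The primary outcomes (time to A&E attendance, 28-day emergency readmission, time to readmission) are not shown to be affected. The rule deserves correction because it is explicit and cheap to change; it does not threaten the study's main comparisons.

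**What to change.** Add to the Confounding variables paragraph:

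- **Outcome 10 (in-patient cost):** HRG is not a covariate. Adjust for age, sex, comorbidity and prior hospital use from HES history, reason for admission based on diagnosis, and method of admission.
- **Outcome 2 (length of stay):** report estimates with and without HRG, and state that the first compares stays within HRG while the second includes any effect through a change of HRG.
- **Readmission, A&E and mortality outcomes:** keep HRG as a case-mix covariate, and state that it is the HRG of the index admission.

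The cost is a few sentences and one extra length-of-stay model. Case-mix control for the cost outcome becomes slightly coarser. The HES variable list in Box 5 of Appendix One shows method of admission but no admission diagnosis, so the data request must be checked for diagnosis fields. The comorbidities that the protocol already plans to derive from HES need those fields in any case.

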1. **Unconsented data:** SIHHC (hospital discharge projects) taking part in the study (Sites 1-2, 7-13 using clinically led services; Sites 3-4, 14-20 using non-clinically led services) will be asked to provide identifying and demographic data (forename, surname, aliases, date of birth, sex, current or previous postcodes, nationality, ethnicity, NHS number) for service users during the period November 2013 to a maximum of November 2016. However, note that for some services we will collect data that ends before 2016 as some will have been shut down before this time period and in some we may collect data at an earlier point, providing we receive the appropriate permissions and ethical and CAG approvals.
2. **Consented data from a subset of study fieldwork sites (n=6 sites):** We will collect data on 252 individuals across 4 sites with SIHHC (hospital discharge) schemes (two sites that are clinically led (Sites 1&2), two sites that are non-clinically led (Sites 3&4)) and on 126 individuals across two sites with standard /usual care (Sites 5&6), giving 378 individuals in total (63 per site x 6 sites). The data collection for this part of the work is contained in a baseline, exit and 3-month follow up data questionnaire and will collect information on demographic information, along with dates of contact with SIHHC services, past use of health and social care services, mental health services, smoking, alcohol, and drug taking history, prison and homeless history, employment, user satisfaction with service delivery, and data on quality of life (EQ5D). The voluntary sector hospital discharge projects will be asked to help collect this data on behalf of the research team as part of their routine outcomes monitoring and will be reimbursed for doing so at a rate of £20 per completion. The data flow chart shows how this work will be integrated with WP1 for practical purposes.
3. The data flow chart shows how this work will be integrated with WP1 for practical purposes.

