A second cost utility analysis will also be performed. This model will also take an NHS perspective and use costs based on HES data as for the cost effectiveness model, but additionally will use outcomes based on QALY data (primary EQ5D data collected through the field work in a subgroup of SIHHC users at baseline and three month follow up). Data from the two types of service will also be compared to each other and homeless controls from a wider London based survey of 455 homeless individuals accessing Find and Treat screening service for tuberculosis. QALY loss due to morbidity and mortality averted will be examined. Cost estimates will be based on HES data and calculated at two time points: baseline, including retrospective data up to 3 month prior enrolment in the study, and follow up, including prospective data up to 3 month service follow up. Outcome data (QALY) will be calculated from EQ5D data collected at baseline and 3 month follow up.

Cost and effectiveness estimates to be calculated for one year follow up period after entering the study with simulations to 20 years and costs will be discounted at 3.5% per annum. A sensitivity analysis will be carried out in order to examine uncertainties within the cost effectiveness and utility model to examine the uncertainty within the parameters used.

A third cost utility analysis will also be performed using costs and health outcome (consented) data collected from the 6 case study sites. This model will take an NHS and also a wider public sector perspective (e.g. exploring costs for use of social care, prison, supported housing etc.).

The added value of this third economic analysis would be to estimate the cost utility of hospital discharge services from a larger public sector perspective whilst incorporating contextual information from the realist evaluation into the economic evaluation.

The objective of this economic evaluation will be to:

- Evaluate the effect of SIHHC on access to resources and their attached costs (health and mental health services, drug and alcohol services, social care services, housing situation) and on individual wellbeing, and how effect may vary across schemes in different sites
- Compare the effect of SIHHC on access to resources and individual wellbeing to sites relying on standard provision only (i.e. those that do not have access to SIHHC)
- Evaluate any variation in effect of SIHHC across time (dependent on opportunities for tracking participants over the longer term)

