Unique Study ID created for
 Each individual record and left
 On site

Box 5: Data variables collected for WP2:**Linked HES / ONS data variables requested**

Field name (where known)	Description of contents
admidate	Date of admission
elecdate	Date of decision to admit
admimeth	Method of admission
admisorc	Source of admission
firstreg	First regular day or night admission
elecdu	Waiting time
disdate	Date of discharge
disdest	Destination on discharge
dismeth	Method of discharge
DISREADYDATE	Discharge ready date (delay in discharge)
ARRIVALDATE	Arrival date
AEATTENDCAT	Attendance category
AEATTENDDISP	Attendance disposal
TREAT2_N	treatment
APPTDATE	Appointment date
ATTENDED	Attended or did not attend
TRETSPEF	Treatment specialty
cause_of_death	Original underlying cause of death
cause_of_death_non-neonatal	Non-neonatal cause of death mentions
	Match rank (ranking of quality of match)
dod	Date of death

SIHHC data variables

Other than the demographic information, we expect few sites to contain all the data variables listed below, but where they are (and for example we know of several sites that collect EQ5D data on all service users) we will collect these unconsented data. The list below therefore provides a potential list of variables we would attempt to collect at each site.

Example field name (where known)	Description of contents
date_interviewed	Date of interview
first_name	First name
surname	Surname
middle_names	Middle names (s)
Alias	Any alias names
sex	Sex of individual
address1	Address line 1
address2	Address line 2
address 3	Address line 3
postcode	postcode

telephone	Home telephone number
mobile	Mobile telephone number
plbirth	Place of birth
ethnicity	Ethnicity
Date_admission	Date of hospital admission
Ad_diagnosis	Admitting diagnosis
Date_discharge	Date of hospital discharge
sympwloss	Currently has symptoms of weight loss for no reason
sympcough3w	Currently has been coughing for more than 3 weeks
sympfevns	Currently has fever or night sweats
symphaemopt	Currently is coughing up blood
sympsob	Currently has shortness of breath
symprone	Currently has none of these symptoms
gpyeslocal	Registered with Local GP
gpnotlocal	Registered with GP that is not local
noreggp	Not Registered to GP
ae_visits	Number of A&E visits in the last year
op_visits	Number of hospital outpatient user visits in the last year
hospitalisations	Number of hospitalizations in the last year
vaxhepb	Individual been vaccinated against Hepatitis B

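### The first two economic models claim an NHS perspective, but their cost source (linked HES plus scheme costs) cannot capture GP or community NHS care

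*Protocol*

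**What the plan says.** The Health Economics Analysis section of the protocol sets out three models.

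- **Primary (cost-effectiveness).** "This model will take an NHS perspective, with costs based on the linked HES data analysis". Costs use national tariff figures and are to cover "length of hospital stay, emergency admissions, and fixed and variable costs estimates for each of the SIHHC services".
- **Second (cost-utility).** "This model will also take an NHS perspective and use costs based on HES data as for the cost effectiveness model". The timing is also tied to that source: "Cost estimates will be based on HES data and calculated at two time points".
- **Third (cost-utility).** This uses consented data from the six case study sites and takes both an NHS and a wider public sector view. Its objectives name health, mental health, drug and alcohol, social care and housing resources.

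Under Data linkage, the records are sent for linkage "to provide data on hospitalisations and A&E attendances and deaths for individuals in the 20 sites and Find and Treat database". Box 5 of Appendix One adds hospital appointment fields, such as "Appointment date". The consented questionnaires (Data sets used for WP2, item 2) are said to cover "past use of health and social care services, mental health services, smoking, alcohol, and drug taking history", among other items.

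**The concern.** An NHS perspective should count NHS care wherever it is given. HES linkage supplies hospital care, and the scheme budgets supply the cost of the schemes. Neither source holds GP consultations, community mental health care or NHS drug and alcohol care.

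This matters because the background sections describe the schemes as routes into that care. The Liverpool nurse-led team passes people to a specialist primary care centre with GP, alcohol and hepatitis C staff. The Pathway teams aim to hand people on to other services. Housing link workers refer to further support. A hospital-only costing can record a fall in readmissions without recording the community care that may have helped to produce it. Objective 3, which this work package is meant to answer, asks about service use and cost across the whole system. A commissioner who reads an NHS-perspective result from the primary model would take it as wider than it is.

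**Working it through.** The documents give no unit cost or rate of use for the omitted care, so no stated figure can be reproduced. The check compares the stated scope with the data sources.

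**1. What each model can cost**

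- Primary: linked HES plus the fixed and variable costs of the schemes. There is no non-hospital NHS item.
- Second: HES costs on the same basis as the primary model, over three months before and three months after enrolment. There is no non-hospital NHS item.
- Third: service use from the consented sample, multiplied by unit costs. Non-hospital items are named.

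**2. Could HES supply the missing items?** The linked content is admissions, A&E attendances, appointments and deaths. No primary care, community mental health or drug and alcohol dataset is linked. The protocol does not say whether mental health inpatient stays are captured, so for mental health the gap is certain only for community care.

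**3. Would the planned sensitivity analysis reveal the gap?** It examines uncertainty in the parameters used. A cost category that is absent from the model is not a parameter and would not be varied.

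**4. Does the third model feed the other two?** Nothing in the text says so.

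**5. Scale, under assumptions.** The figures for omitted cost, hospital saving and QALY gain below are assumed.

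- Per service type: the protocol's 90 users a month over 24 months gives 90 × 24 = 2,160 users. An omitted £100 per user is 100 × 2,160 = £216,000.
- Savings: with an assumed hospital saving of £500 per user and omitted extra care *c*, the true saving is 500 − *c*, and the overstatement is *c* / (500 − *c*). For *c* = £100 this is 100/400 = 25%. For *c* = £400 it is 400/100 = 400%.
- Cost per QALY: omitted cost *c* with QALY gain *q* raises the ratio by *c*/*q*.

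| Assumed *q* | *c* = £100 | *c* = £250 | *c* = £500 |
|---|---|---|---|
| 0.01 | £10,000 | £25,000 | £50,000 |
| 0.02 | £5,000 | £12,500 | £25,000 |
| 0.05 | £2,000 | £5,000 | £10,000 |

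For comparison, the protocol's footnote on the earlier Pathway trial gives £26,000 per QALY. The omission could therefore be small or decisive, and the documents cannot say which.

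**6. Direction between scheme types.** The King's Health Partners Pathway team has GP sessions and mental health practitioners in its own staffing, so that care would enter as scheme cost. Housing link workers give no clinical input and refer on, so NHS care reached that way would be uncosted. On the other hand, clinically led teams also hand people on to outside services. The net effect cannot be signed from the text.

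**The case against.** The strongest reply is that the protocol is open about its source and covers the wider costs elsewhere. The primary model rests on unconsented hospital linkage with readmission outcomes, so hospital costing suits its design. The third model costs the wider services at all six sites and assesses the standard-care sites in the same way as the specialist ones. This stands, and a reader should not infer that the protocol ignores community care altogether. It does not rescue the NHS label on the first two models, one of which is the primary analysis.

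Three stronger readings are tempting, and the documents do not support them.

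- *A&E and outpatient costs are left out.* The cost list is introduced as what the estimates will include, so it is open. A&E attendances are part of the linked data and the appointment fields are requested. The wording needs clarifying, but no omission is shown.
- *The models are biased towards the schemes, and more so for the type that refers more.* This requires schemes to raise community use above that of controls. The protocol states referral as an aim and gives no rate. Controls also use community care, which is equally uncosted.
- *The missing items are already collected and can simply be added to the second model.* That model also compares scheme users with 455 Find and Treat controls. The variables listed for Find and Treat in Box 5 are identifiers, venue, screening outcome and EQ-5D, with no service use. Adding questionnaire costs for scheme users alone would charge one side for care that is free on the other. Availability is also only partly shown. The questionnaire is described in general terms, with drug and alcohol items worded as history. The itemised list of data sought from schemes has GP registration but no GP visits, and no count of drug or alcohol treatment contacts.

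**Conclusion.** The point holds as a mismatch between the stated perspective and the cost source. As written, models one and two deliver hospital and scheme costs, and the protocol provides no source that would widen them to the NHS as a whole.

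The consequence is conditional. If the schemes increase GP, community mental health or NHS drug and alcohol care relative to the comparator, NHS savings are overstated by the cost of that increase. The size is unknown, and every monetary illustration above rests on assumed inputs. No direction can be claimed for the comparison of clinically led with non-clinically led schemes. The matter should be corrected because it limits what the primary economic result can conclude.

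**What to change.** 1. In the Health Economics Analysis section, restate the perspective of the primary and second models as hospital and scheme costs. State that A&E and outpatient costs from HES are included. Refer to the third model for the wider NHS result.
2. Add a scenario analysis to models one and two that applies an incremental non-hospital NHS cost per user, taken from the third model's consented resource-use data. Use sites 1-4 versus sites 5-6 for specialist against standard care, and sites 1-2 versus sites 3-4 for clinically led against non-clinically led. Leave out contacts with the scheme's own staff, which are already counted as scheme cost. State how a three-month increment is carried to one year.
3. Do not add questionnaire costs to scheme users alone in the comparison with Find and Treat controls. If the scenario is used there, state the assumption that the standard-care sites stand in for those controls.
4. Before relying on this, the sponsor should confirm that the questionnaire counts GP contacts and drug and alcohol service contacts.

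The cost is a change of wording plus reuse of costing already planned for the third model. The limits are that the increment comes from a consented subset (252 people planned at sites 1-4 and 126 at sites 5-6), with mainly three-month follow-up and some missing answers to be expected. The savings figure may also become less favourable.
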